**Aim 3:** To examine if changes in the following potential mechanisms of change variables mediate treatment effects (e.g., Step One and standard TF-CBT) on child PTSS and impairment: (a) fear habituation: decreases in child’s fear-based arousal; (b) cognitive changes: reductions in child’s negative trauma-related cognitions; (c) inhibitory learning: child’s decrease in expectancy of negative outcomes; and (d) fear toleration: extent of child’s toleration of fear activation.

**3.1. Hypothesis:** Decreases in children’s fear-based arousal, improvements in negative trauma-related cognitions, decreases in children’s expectancy of negative outcomes, and changes in fear toleration over time will mediate Step One and standard TF-CBT treatment outcomes in PTSS and impairment.

**3.2. Secondary Hypothesis:** The mechanisms of change (e.g., a, b, c and d in Aim 3) will occur during all components of treatment but greater changes in these processes will occur during more direct exposure activities (e.g., imaginal and *in vivo* exposure in Step One) than less direct exposure activities (e.g., developing a trauma narrative in Standard TF-CBT) and during coping skills in both treatments.

**Aim 4:** To examine the economic cost of delivering SC-TF-CBT versus standard TF-CBT.

**4.1. Hypothesis:** Stepped Care TF-CBT will be more cost-effective than standard TF-CBT.

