**c.9. Sample Size Considerations and Power Analyses.** We will enroll a total of N=216 subjects with a 1:1 randomization between SC-TF-CBT and standard TF-CBT. Based on our successful track record in obtaining post and follow-up data in our R34 SC-TF-CBT trial (only 3.77% missing post- data, and 6.1% missing 3-mo. follow-up data, N=53), and the PIs previous child trauma clinical trial with a 1-year follow-up (8.57% attrition), we conservatively anticipate 15% attrition at post-assessment resulting in 184 subjects (92 per group) and a 10% lost to follow-up at 6- and 12-months resulting in 166 subjects (83 per group) and 150 subjects (75 per group), respectively. Sample size requirement was determined by CEA for Primary Aim 4 and it also provides sufficient power for Primary Aims 1 to 3 under various assumptions. **Primary Aim 1**, Hypothesis 1.1, the study will have 80% power to show that SC-TF-CBT is at least as effective as standard TF-CBT. This assumes an alpha of .05, sample size of 92 per group after attrition and a difference of 0.41 SD units or less as unimportant. We expect to maintain the same power of 80% in testing the hypothesis (1.2.) that focuses on the outcomes at follow-up (6- and 12-months). Though we may lose an additional 10% of participants at each follow-up point, reduction in measurement error through repeated measures and use of multiple imputation method will mitigate the sample size loss. For **Primary Aim 2**, 80% power will be achieved for detecting responding rates difference between 62% and 30%, 72% and 40%, or 80% and 50%. This assumes that we divide the patients into two equal size groups based on the tailoring variable value with a total of 92 patients (SC-TF-CBT condition only). For **Primary Aim 3**, we will have >80% power to detect a small to moderate effect (0.29) in a unidirectional bivariate latent different score model with complete longitudinal observation for the 184 children under both conditions (for analyses involving CPTCI, the detectable effect size is 0.33). For the secondary hypothesis 3.2., we have moderate power (.57) to detect different strengths of the unidirectional prediction between the two conditions (e.g., 0.15 vs 0.45 or .00 vs .30; for the CPTCI, the power for the same comparisons is .55). For **Primary Aim 4**, the study will have 80% power to detect cost differences between SC-TF-CBT and standard TF-CBT, assuming medium effect size (.5), an alpha of .05 and sample size of 92 per group. The sample size will also be sufficient to maintain 80% power to detect a medium effect size for children with low values for the tailoring variable, and to detect a large effect size for children with high values.

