## Amendment to the analysis plan 2.11.2022

**Aim 1.** We applied linear mixed-effect models (LME; SAS Institute Inc, 2015) with repeated measures to detect whether the two treatments performed differently at post-, 6- and 12-month assessments. Instead of 5% alpha we used a more stringent 2.5% alpha (Piaggio et al, 2012) for the non-inferiority analysis with the .41 margin. For the non-inferiority margin for the PCL-5, the clinically significant change threshold is 10 points although adult PTSD trials have used -5 (Foa et al., 2019) to -10 (Mathersul et al., 2019) points. We used -8.8 as the margin which was based on an expert panel and prior studies with adults (Acierno et al., 2017). Due to attrition (27.87%) being higher than planned (15%) and enrollment (N = 183) lower than the planned enrollment (N = 216), the power analysis was based on the actual randomization of 183 participants (SC-TF-CBT=91; standard TF-CBT=92).

**Aim 2.** We used backward stepwise logistic regression with predictors with  $p < .01$ . Besides predictors in the unadjusted model, demographics including children gender, age and race were included in the partially adjusted

model. In addition, three child primary outcomes were added for the full adjusted model.

**Aim 3.** Instead of LDS we used Linear mixed-effect models (LME) with repeated measures were used to detect whether the potential mechanisms of change declined significantly over time and whether the rate of change differed by treatment group with standard TF-CBT coded as 0 and Step One responders coded as 1. Further, we tested mediation and moderated mediation. If moderated mediation was not found mediation was tested with two regression equations: the first equation included mediators regressed on treatment condition and outcome variables at baseline; the second equation included outcomes regressed on treatment condition, mediators, and outcome variables at baseline. If there was no evidence of significant mediation, linear regression model (OLS) was applied to test the linear estimates as predictors for both outcome (TSCYC-PTS and CSDS-P).

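### Amended Aim 3 falls back to one mediator-outcome slope for both treatments whenever the moderated-mediation test is not significant, although tests of that kind have little power here, so a link present in one treatment can be carried as common to both

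*Combined protocol and SAP*

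**What the plan says.** Aim 3 of the Amendment to the analysis plan 2.11.2022 replaces the latent difference score (LDS) models of section c.8.3 with linear mixed models and regression. The groups compared are "standard TF-CBT coded as 0 and Step One responders coded as 1". Mediation and moderated mediation were both tested, and the next step depends on the result: "If moderated mediation was not found mediation was tested with two regression equations".

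The first equation regresses the mediator on treatment and the baseline outcome. For the other, "the second equation included outcomes regressed on treatment condition, mediators, and outcome variables at baseline". No treatment-by-mediator term is listed. A further fallback follows: "If there was no evidence of significant mediation, linear regression model (OLS) was applied to test the linear estimates as predictors for both outcome". No treatment-specific slope is stated there either. The amendment does not name the moderator, the alpha level or the criterion for moderated mediation being found.

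Hypothesis 3.1 in section 2 is about both treatments: "changes in fear toleration over time will mediate Step One and standard TF-CBT treatment outcomes in PTSS and impairment".

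Section c.9 gives the only power figure for a between-treatment difference in mechanism strength: "we have moderate power (.57) to detect different strengths of the unidirectional prediction between the two conditions". The effect sizes are "0.15 vs 0.45 or .00 vs .30; for the CPTCI, the power for the same comparisons is .55". The figure belongs to secondary hypothesis 3.2 under the LDS model. Aim 3 power was computed "with complete longitudinal observation for the 184 children under both conditions", which is 92 per group. The amendment gives no new power figure for Aim 3, although it changes the model, reports 183 randomized and 27.87% attrition, and restricts one group to Step One responders.

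**The concern.** The branch lets a non-significant test choose the model. When the test misses a real difference, the fallback equation estimates a weighted average of two unequal slopes, which describes neither treatment. No confidence limit or margin on the difference is required before the slopes are merged.

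The plan itself expects that the treatments may differ. Sections a.4 and c.8.3 describe exposure as more direct in Step One than in TF-CBT, and section b.2 wants to explore mechanisms that differentiate the two delivery approaches. Section a.4 also says that clinicians would target and monitor these processes within each treatment. If a link that operates only in Step One is carried by a common coefficient, it may be taken as relevant to TF-CBT as well, and the reverse.

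**Working it through.** **Inputs.** Slope pairs 0.15 vs 0.45 and .00 vs .30, 92 per group, power .57 (section c.9). 183 randomized, 91 and 92 by arm, 27.87% attrition (amendment). Pilot Step One response 77.6% (section c.1.3). Assumptions: two-sided alpha .05, which is not stated for Aim 3; treatment is the moderator, being the only grouping variable in the amended Aim 3 text.

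**1. Reproducing .57.** Wald test of two standardized slopes:

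power = Φ( |b1 − b2| / √[(1 − b1²)/(n1 − 2) + (1 − b2²)/(n2 − 2)] − 1.96 )

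- 0.15 vs 0.45, 92/92: SE = √(0.9775/90 + 0.7975/90) = 0.140; 0.30/0.140 = 2.14; power .57.
- .00 vs .30, 92/92: SE = √(1/90 + 0.91/90) = 0.146; 0.30/0.146 = 2.06; power .54.

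The plan's figure reproduces for the first pair and comes out 3 points lower for the second. The miss rate is 1 − .57 = 43% to 1 − .54 = 46%. A Fisher-z version gives power .60 and .54.

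**2. Sizes after the amendment (assumed).** Even attrition: 92 × 0.7213 = 66.4 and 91 × 0.7213 = 65.6, so about 66 per arm. Responders at the pilot rate: 65.6 × 0.776 = 50.9, so about 51.

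| Sizes | Power, 0.15 vs 0.45 (Wald; Fisher) | Power, .00 vs .30 (Wald; Fisher) |
|---|---|---|
| 92 vs 92 | .57; .60 | .54; .54 |
| 66 vs 66 | .44; .46 | .41; .41 |
| 66 vs 51 | .39; .41 | .37; .37 |

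At 66 vs 51 the difference is missed about 59-64% of the time.

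**3. What the common slope then shows.** Simulation, 8,000 runs per case: test the treatment-by-mediator term at .05; if it is not significant, test the common mediator slope at .05. True slopes are 0 in one treatment and .30 in the other.

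| Sizes (TF-CBT vs Step One) | Slope of .30 in | Difference missed | Missed and common slope significant |
|---|---|---|---|
| 92 vs 92 | Step One | 45% | 24% |
| 92 vs 92 | TF-CBT | 47% | 25% |
| 66 vs 51 | Step One | 64% | 19% |
| 66 vs 51 | TF-CBT | 63% | 29% |

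A repeat with new seeds gave up to 30% in the last row. The two 66 vs 51 rows differ because the common slope is weighted by group size: about .30 × 51/117 = .13 when the link is in Step One and .30 × 66/117 = .17 when it is in TF-CBT.

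**4. Requiring both equations.** A mediation finding also needs treatment to affect the mediator in the first equation. Adding that test at .05 to the same sequence gives:

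| Treatment difference in mediator | 92 vs 92 | 66 vs 51 |
|---|---|---|
| none | 1% | 1% |
| 0.2 SD | 7% | 4-5% |
| 0.3 SD | 13% | 7-11% |
| 0.5 SD | 23% | 15-22% |

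The documents give no expected treatment difference in any mediator, so this rate can only be stated as a range, about 1% to 23%.

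**The case against.** Several points on the other side are sound.

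- **Pooling predates the amendment.** Section c.9 powers the main Aim 3 analysis on all 184 children together, leaves between-treatment strength to a secondary hypothesis, and says openly that power for it is only moderate. Hypothesis 3.1 predicts the mechanisms in both treatments, so a common slope is a natural model, and the amendment adds a moderation check. This stands. It does not answer how a non-significant check should be reported.
- **The .57 is not the power of the amended test.** It was computed for LDS models under hypothesis 3.2. A reader might take it as the power of the moderated-mediation test; the documents do not support that. It serves as the plan's own guide to how hard such differences are to detect.
- **The text draws no conclusion of equality.** A reader might infer that the plan treats a non-significant test as proof that the mechanisms are the same. The amendment says no such thing, and it has no rule for attributing a mechanism to each treatment. In the two equations the indirect effect is itself a contrast between treatments, so a significant one does not say that TF-CBT has the mechanism.
- **The one-in-four rate is not a mediation rate.** It is tempting to read it as the chance of falsely declaring a mediator. It covers only the mediator-outcome slope and, at most, the later OLS predictor step. Step 4 gives the rates when both equations are required.
- **The 66 vs 51 sizes are assumed.** The amendment does not say that attrition was even or applied equally to Aim 3 data. The response rate comes from 49 pilot children, before the new step-up triggers. The 92/92 results do not depend on this.

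**Conclusion.** The concern holds as a weakness in how Aim 3 is analysed and reported. As written, a non-significant moderation test leads to a single mediator-outcome slope for two treatments about which Hypothesis 3.1 makes separate claims. A difference of .30 is missed about 43-46% of the time at the planned size, and about 59-64% at 66 vs 51. With slopes of 0 and .30, a significant common slope after a missed difference arises in about 24-25% of trials at 92/92 and 19-30% at 66/51. The chance that this becomes a declared mediation is about 1% to 23%.

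These results assume two-sided .05 tests, treatment as the moderator, standardized slopes and, for the smaller sizes, even attrition with the pilot response rate. The Aim 1 comparison is not affected.

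**What to change.** For each mechanism and each outcome (TSCYC-PTS and CSDS-P), whatever the moderation p-value, report from the model with the treatment-by-mediator term:

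- the mediator-outcome slope in standard TF-CBT, with a 95% confidence interval;
- the slope in Step One responders, with a 95% confidence interval;
- the difference between the two, with a 95% confidence interval.

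Describe the within-arm slopes as associations, because there is no treatment contrast within an arm. State the moderator and the criterion used for moderated mediation. Add a sentence saying that a non-significant moderation test does not show the same mechanism in both treatments. The common-slope result can stay beside these estimates.

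I would not go further and allow a mechanism to be claimed only from a treatment's own interval. With 51 children the power for a correlation of .30 is about 57% (Fisher z: 0.3095 × √48 − 1.96 = 0.18), and such a rule invites comparing one significant arm with one non-significant arm.

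The cost is a wording change and re-output. The amendment is written in the past tense, so the data and models should be in hand. The downside is that treatment-specific intervals are wider than a pooled one.

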**c.1.2. Candidate First-Stage Tailoring Variables.** An exploratory aim of the R34 was to explore differential characteristics of Step One responders/non-responders to identify potential first-stage tailoring variables. Based on prior literature and our clinical experience, we first explored differences in child variables (PTSD symptoms, internalizing and externalizing problems, depression, polytrauma (>1 traumatic event), interpersonal/non-interpersonal trauma, and age), parent variables (PTSD, depression and parenting stress) and environmental factors (treatment barriers) between Step One responders/non-responders. Two measures that showed substantial differences between responders and non-responders were internalizing problem T-scores and critical life events regarding barriers to treatment. We further applied classification tree method[78] to find the optimal cutoff values that maximally distinguished responder/non-responders after Step One. Regarding total internalizing T-scores, those children (16/49=32.7%) with a score >71 had a response rate of 56.3%, and those with a score ≤71 had a response rate of 87.9% ( $X^2=6.19$ ,  $p=.01$ ). Regarding critical life events, those children

(28%) with a score  $>16$  had a response rate of 44.4%, and those with a score  $\leq 16$  had a response rate of 82.6% ( $X^2=4.66, p=.03$ ). We recognize that given the small sample size, some of the results did not reach significance especially when adjusting for multiple comparisons. However, high internalizing problems is consistent with the literature suggesting that these children may need more intensive treatment [79, 80] and our qualitative findings are consistent with critical life event barriers as a theme for Step One non-responders. We considered externalizing problems as a first-stage tailoring variable since non-inferiority was not supported; however, there was not a significant difference between responders/non-responders and externalizing problems after Step One; nor was there a clear significant optimal cutoff value. Further, since GLM results and percentages of those above the clinical cutoff revealed no significant differences between SC-TF-CBT and TF-CBT at post- and follow-up, the evidence did not support externalizing problems as a tailoring variable. These results provide suggestive evidence of effect moderation and a preliminary establishment of candidate first-stage tailoring variables to be tested in the proposed application.

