The third time-varying variable that was piloted is the response/nonresponse criteria after Step One. Of the 49 patients across both pilot studies who completed an assessment after Step One, 38 (77.6%) responded after Step One (see b.2. for responder status criteria). Congruency between responder status criteria and parents’ thoughts about if more treatment was needed was as follows: 75.5% congruent, 20.4% incongruent (with one parent wanting to end when more treatment was recommended), and 4.1% unsure. As per our pilot protocol, parents who think more treatment is needed after Step One are offered two additional sessions, and if a child relapses after the maintenance phase, they can step up (no child stepped up after the post-assessment). Given these results, we will use the same responder status criteria derived from our pilot work.

**c.1.4. Cost Measures and Preliminary Costs of Delivering Stepped Care and TF-CBT.** The R34 stepped care grant: 1) piloted data collection methods on the costs of delivering SC-TF-CBT and TF-CBT, and 2) conducted a preliminary comparison of costs associated with delivering SC-TF-CBT and TF-CBT. These cost methods were incorporated into the SC-TF-CBT trial with older children. 1) *Costs Characteristics Information (CCI)*[82] consists of 11 items to measure estimated costs such as out-of-pocket expenses for treatment, lost income due to missing work to attend therapy, patient time associated with treatment, and other cost-related information. We have been successful capturing these cost-related data and procedures for collecting missing data regarding parent’s co-pay have been established. 2) *The Therapist/Patient Time Tracking System (TTTS)*[83] measures the therapist time associated with 14 types of treatment delivery activities (e.g., therapist meetings, phone support, documentation) and parent/child time associated with 9 types of treatment participation (e.g., therapist meetings, phone support, homework). The Service Assessment for Children and Adolescents (SACA)[84] will be administered to track other services used and estimated costs of other services. These cost measures will be used in the proposed study to address the next important step of examining the economic cost of delivering SC-TF-CBT and standard TF-CBT (Aim 4). Also, if tailoring variables effectively distinguish child

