**Within session ratings.** Parents will rate fear toleration and negative expectancy after each trauma-related activity in therapy sessions and parent-child meetings. As in previous NIH-funded clinical trials (PI: [name], study therapist [name], R34MH070827-01A1; 1RC1MH-088969-01), therapist-directed sessions will be video taped. We will systematically identify the child’s participation in the trauma-focused activity within each session and have parents review that segment via video (~15 min.) during the beginning of the time when the parent meets with the therapist. These research procedures will not significantly influence treatment outcome as discussing with the parent what the child completed in therapist-led sessions is current protocol for both treatments, and similar procedures have been used in previous trauma-focused clinical trials with children 3-12. This procedure allows the parent to have direct observation of the child and allows the parent time to process the observations with the therapist. Viewing video segments will not be needed when there are conjoint sessions. For the at-home parent-child meetings, the parent will complete the ratings immediately after the meetings. Children will complete the *CPTCI* at the beginning of Weeks, 0, 2,4 in Step One & 0,5,8 in TF-CBT and the SUDS rating during treatment. For Step One, measures will be in the parent’s *Stepping Together* book, and therapists will collect these measures at each meeting and will remind parents about the measures during the phone meetings. Since Step One and TF-CBT occur within different timeframes (6wks vs. 3mo), the physiological measures will be administered based on when components are covered and during scheduled in-office visits for Step One patients: at session 1, after the coping skills components, and after four exposures in Step One or the trauma narrative in TF-CBT (Table 1). The frequency of four potential mechanism of change measures (e.g., fear based arousal measure (subjective unit of distress), trauma-related negative appraisals, expectancy of negative outcomes, and fear toleration) will be 12 for both conditions. Step One patients will not complete these measures during parent-child meetings 1 and 2 as these meeting occur directly after the first therapist meeting.

**c.6.7. Fidelity Measures.** All of the fidelity measures were successfully utilized in the pilot trials of SC-TF-CBT.

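### The amended Aim 3 mediation equations adjust for the baseline outcome but not for the mediator's own baseline, so starting differences in the mediator can be mistaken for mediation

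*Combined protocol and SAP*

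**What the plan says.** Under Aim 3, the Amendment to the analysis plan 2.11.2022 drops the latent difference score models of section c.8.3. It first uses linear mixed models for change over time, with "standard TF-CBT coded as 0 and Step One responders coded as 1". It then tests mediation and moderated mediation. Where moderated mediation is absent, two regressions are used:

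- Mediator equation: "the first equation included mediators regressed on treatment condition and outcome variables at baseline".
- Outcome equation: "the second equation included outcomes regressed on treatment condition, mediators, and outcome variables at baseline".

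If mediation is not significant, a "linear regression model (OLS) was applied to test the linear estimates as predictors for both outcome". The amendment does not say whether the mediators in the two equations are levels, change scores or slopes. It does not repeat the responder coding for the mediation step.

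On available baselines, Table 1 (section c.6) schedules heart rate and skin conductance (HR/SC) at weeks 0, 2 and 4 in Step One and 0, 5 and 8 in TF-CBT. Section c.6.6 schedules the CPTCI "at the beginning of Weeks, 0, 2,4 in Step One & 0,5,8 in TF-CBT". The distress ratings (SUD), expectancy ratings (ENOs) and fear toleration ratings (CFT) are collected during sessions or parent-child meetings. Section c.6.6 says Step One families skip them at parent-child meetings 1 and 2.

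**The concern.** Each equation names the outcome's baseline and neither names the mediator's. This matters for both paths.

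- **Treatment to mediator (a path).** If the group variable is the one stated for the mixed models, the contrast is a post-randomisation subset against a group with no such restriction. Responders may start with less arousal or fewer negative cognitions. If the mediator is entered as a level, part of that starting gap persists and is read as an effect of Step One.
- **Mediator to outcome (b path).** This path is not randomised under any coding. A child's starting mediator level can influence both the later mediator and the later outcome. The baseline outcome captures this only in part.

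Hypothesis 3.1 is about decreases in arousal, cognitions and expectancy, so each mediator needs to be referred to where it started. Latent difference score models built change in the mediator into their structure, and the amendment names nothing that replaces it.

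**Working it through.** The documents state no figure on this point, so there is none to reproduce. The check asks whether responder selection plausibly shifts baseline status, what that does to the listed equations, and what remains if the groups are the randomised arms.

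**1. Does selecting responders shift baseline status?** In the pilot, "38 (77.6%) responded after Step One" out of 49 (section c.1.3). Section c.1.2 reports that those "with a score >71 had a response rate of 56.3%, and those with a score ≤71 had a response rate of 87.9"%.
- Internalizing: 9/16 = 56.3% and 29/33 = 87.9%. Chi-square = 49 × (9×4 − 7×29)² / (16×33×38×11) = 6.19, matching the stated value. Keeping responders only moves the high-score share from 16/49 = 32.7% to 9/38 = 23.7%.
- Critical events: counts of 4/9 and 19/23, inferred from the stated percentages, give chi-square 4.66, again as stated. The high-score share moves from 9/32 = 28.1% to 4/23 = 17.4%.

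So responder selection does shift baseline status. Neither variable is itself one of the four mediators.

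**2. Direction of the bias.** Let g be the baseline mediator gap left after adjusting for the baseline outcome, r the mediator's stability over time, and the true effect zero.
- Mediator as a level: spurious a = r × g.
- Mediator as a change score: spurious a = −(1 − r) × g, which is regression to the mean with the opposite sign.

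**3. Size.** Inputs from the documents: arms of 91 and 92 ("SC-TF-CBT=91; standard TF-CBT=92"), and 77.6% of the stepped-care arm kept as responders (0.776 × 91 ≈ 71). Assumed: r of 0.3 to 0.7, baseline mediator-outcome correlation c of 0.3 or 0.6, graded dependence of response on the baseline mediator, higher mediator scores worse, and no attrition. Each scenario has 1,500 replicates. False mediation means both paths significant at two-sided 0.05. Monte Carlo error near 5% is 1.96 × √(0.05 × 0.95/1500) = 1.1 percentage points. Selected scenarios:

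| r | c | baseline gap (SD) | level, as written: a; false mediation | change score, as written: a; false mediation | baseline mediator added: a; false mediation |
|---|---|---|---|---|---|
| 0.5 | 0.3 | −0.14 | −0.045; 5.3% | +0.052; 5.2% | +0.003; 4.9% |
| 0.5 | 0.3 | −0.28 | −0.120; 12.0% | +0.122; 9.8% | +0.001; 5.2% |
| 0.5 | 0.6 | −0.30 | −0.088; 9.3% | +0.085; 7.7% | −0.001; 5.2% |
| 0.7 | 0.3 | −0.13 | −0.063; 8.0% | +0.030; 3.1% | +0.003; 5.8% |
| 0.7 | 0.3 | −0.28 | −0.172; 21.0% | +0.070; 4.9% | −0.002; 4.0% |
| 0.7 | 0.6 | −0.30 | −0.122; 14.9% | +0.050; 5.6% | −0.001; 5.1% |

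The formulas agree. In the fifth row g = −0.172/0.7 = −0.246, which predicts a change-score bias of 0.3 × 0.246 = +0.074, against +0.070 simulated.

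Over all scenarios with gaps of 0.13 to 0.30 SD, false mediation is 5% to 21% for levels and 3% to 13% for change scores. With no selection on the baseline mediator it is 4% to 5%. With the baseline mediator in both equations it is 4.0% to 6.3%, and levels and change scores then give the same a path. Slopes were not simulated.

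**4. What the covariate does not repair.** If response also depends on how the mediator moves during Step One, the adjusted a path stays at −0.12 to −0.21 SD and false mediation at 14% to 36%.

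**5. If treatment condition means randomised arm.** The a path is then unbiased without the covariate. Adding it lowers that path's standard error by 1 − √[(1 − r²)/(1 − r²c²)], assuming the baseline outcome predicts the later mediator only through the baseline mediator. For r = 0.4, c = 0.6 this is 1 − √(0.84/0.9424) = 6%. For r = 0.6, c = 0.3 it is 1 − √(0.64/0.9676) = 19%. The b path still needs the term.

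**The case against.** The strongest reply is that no bias has been shown. It would need a real baseline gap in the mediator and, on the a path, the responder coding. The documents give no baseline mediator values by group, and the coding sits in the mixed-model sentence. Carrying it into the mediation step is a likely inference, not stated text. The pilot also hints at a small gap. Under normality, a move from 32.7% to 23.7% above a cut is a shift of about 0.27 SD in internalizing. If internalizing correlates 0.3 to 0.6 with a mediator (assumed), the mediator gap is 0.27 × 0.3 = 0.08 to 0.27 × 0.6 = 0.16 SD, where inflation is slight. Section c.1.2 also lists baseline PTSD symptoms among the variables explored, yet names only internalizing and critical events as substantially different.

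A second reply is that slopes were probably meant, given the language about rate of change and linear estimates and the different measurement weeks by arm. Carry-over of a level gap is then the wrong mechanism, and adjusting change for baseline across non-randomised groups is itself disputed.

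Much of this stands. It rules out saying that baseline differences do pass as mediation, and it leaves the size unknown. It does not remove the omission: the mediator-outcome path is confounded by the mediator's start under any coding. If slopes were meant, the amendment should say so.

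A reader might also infer that one covariate makes the responder contrast sound, or that a week-0 value exists for every mediator. Neither is supported. Responders are defined by post-Step One status (section b.2), and SUD, ENOs and CFT have no clear common pre-treatment rating.

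**Conclusion.** The point holds in a limited form. Both listed equations omit the mediator's baseline, although week-0 HR/SC and CPTCI are scheduled in both conditions. This leaves the mediator-outcome path open to avoidable confounding. If the responder coding carries over, it also lets a starting gap distort the a path, in either direction depending on the mediator's scale. The ranges of 5% to 21% for levels and 3% to 13% for change scores rest on assumed gaps, stabilities and correlations. At the smaller gaps the excess is negligible. For CPTCI, given only to ages 6 to 12 (about 78% of the sample, section c.6.5), numbers are smaller than those simulated.

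A reader might infer that any mediation found under this plan is an artefact. The documents do not support that: they give no baseline mediator values by group and do not define the mediator variable. Selection of responders on post-baseline status is the larger threat, and it is separate from the missing covariate.

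**What to change.** 1. Add the week-0 mediator value to both equations for HR/SC and CPTCI, beside the baseline outcome.
2. For SUD, ENOs and CFT, do not treat a first in-treatment rating as a true baseline. State what is used, and label those results accordingly.
3. State whether each mediator enters as a level, change score or slope, and how treatment condition is coded in the mediation step.
4. Run the mediation by randomised arm, or label the responder contrast as non-randomised.
5. Report baseline mediator values for the groups compared, so that the size of any gap can be seen.

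The cost is one extra covariate and a rerun, with some loss of cases where the week-0 value is missing. No new data collection is needed for HR/SC or CPTCI.
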